#### [B-cell tolerance defects in MS and other autoimmune diseases](#)

Defects in early B-cell tolerance checkpoints are associated with many autoimmune diseases including MS, type 1 diabetes (T1D), rheumatoid arthritis (RA), pediatric systemic lupus erythematosus (SLE) and systemic sclerosis (SS), and result in large numbers of circulating autoreactive B-cells in the blood of these patients. Early B-cell tolerance checkpoints include a central B-cell selection step in the bone marrow (BM) that is vastly dependent on sensing self-antigen binding to B-cell receptors (BCRs) and most likely Toll-like receptors (TLR),

whereas the peripheral B-cell tolerance checkpoint appears to require functional regulatory T cells (Treg) to prevent the accumulation of autoreactive mature naïve B-cells. In line with these observations, polymorphisms in PTPN22, BLK, LYN, CSK, BANK1 identified by GWAS studies as susceptibility genes for RA, SLE, or T1D but not MS, encode components regulating BCR signaling and likely result in the impaired central B-cell tolerance characteristic of T1D, RA, and SLE. In contrast, people with MS do not display gene

Version: 2.0

Date: 3/8/2019

polymorphisms linked to the BCR signaling pathway and most of these patients establish normal central B-cell tolerance. However, people with MS suffer from an impaired peripheral B-cell tolerance checkpoint, resulting in the accumulation of autoreactive mature naïve B-cells in their blood potentially linked to alterations of their Treg function and IFN-gamma and IL-17 production. Interestingly, IL-17 production by T cells and T follicular helper (Tfh) development is favored by IL-6, a pro-inflammatory cytokine that is secreted with GM-CSF by B-cells from people with MS. Since anti-B-cell therapy normalizes IL-6 production in newly generated B-cells, this regimen may therefore also decrease IL-17 production by T cells including Tregs and circulating Tfh in treated people with MS in remission. In addition, B-cells have been shown to support the maintenance of memory T cells and their elimination may therefore favor the elimination of self-antigen specific T cells secreting inflammatory cytokines. Moreover, transitional B-cells enhanced after anti-B-cell therapy may also secrete increased amount of IFN-alpha, which has been shown to improve the condition of people with MS. We hypothesize that long-term suppression of disease activity in MS is the result of anti-B-cell therapy eliminating autoreactive B-cells in patients' blood and that newly generated B-cells after B-cell repopulation will not contain autoreactive clones associated with autoimmunity, an observation that may correlate with a normalized Treg compartment that no longer secrete inflammatory cytokines. Hence, a short two course of B-cell depletion may correct the peripheral B-cell tolerance defect seen in most people with relapsing MS and this normalization may be responsible for the long-term suppression of disease activity.

## Specific aims and study overview

**Aim1: To determine whether two courses of treatment with ocrelizumab is associated with long-term suppression of disease activity in people with highly active early relapsing MS.**

We hypothesize that only two courses of treatment with ocrelizumab in subjects with early relapsing MS will stop the disease activity, as measured by new T2 or Gd-enhancing lesions on brain and spinal cord MRI, even long after B-cell repopulation in the blood. In an open label unblinded trial, we will enroll 10 patients with relapsing MS and with at least two Gd-enhancing lesions on the brain and spinal cord MRI and treat them with two courses of ocrelizumab and follow them clinically and radiologically for at least two and a half years.

**Aim 2: To test if two courses of treatment with ocrelizumab corrects the B-cell tolerance defects in patients with relapsing MS.** We hypothesize that B-cells repopulating after a two course-treatment with ocrelizumab will NOT contain an elevated proportion of autoreactive clones observed pre-treatment. In the patients recruited in aim 1, we will harvest pre-treatment and post-repopulation peripheral B-cells and assess early B-cell tolerance checkpoints by testing the reactivity of recombinant antibodies cloned from single B-cells.

## Risk/benefit assessment

### Known potential benefits

With stopping ocrelizumab after two courses, participants will be less likely to suffer from immunosuppressive effects of this medication. The long-term safety of this medication is also not known and with limiting the exposure of participants to only two courses of treatment, they will not be exposed to unknown risk associated with long term use of this medication.

Version: 2.0

Date: 3/8/2019

## Known Potential Risks

By limiting the participants to two courses of treatment with ocrelizumab, participants are at higher risk of return of MRI or clinical disease activity. However, it is well within the standard practice to start patients with safer, but less efficacious disease modifying treatments and if the disease activity continued, to escalate to higher efficacy medications. Even in the case of more effective medications such as alemtuzumab, the standard practice is treatment with only two courses of the medication and retreatment if the disease activity returns. In this study, we will restart the treatment with ocrelizumab in patients who experience the return of the disease activity, a practice similar to escalation or retreatment which are standards of care.

Loss of privacy is another risk of participating in this study. Several mechanisms will help prevent loss of privacy. Access to the data will be limited to study personnel and the database will be password-protected. Furthermore, each member of the study team will be limited to only the data they need to perform their tasks so that privacy is protected as much as possible. Only study personnel who need to access the database will be given such access.

The risks associated with the study are minimal, and an adequate protection plan is in place; as such, the potential benefits exceed the potential risks. The participation of patients is completely voluntary; the alternative to the patients is to not participate in the study. Lack of participation will in no way compromise the relationship they have with their neurologists or the ongoing care they receive for their MS.

## Study objectives

### Primary objective

To determine whether two courses of treatment with ocrelizumab is associated with long-term suppression of disease activity in people with highly active, relapsing MS.

### Secondary objective

[figure not shown]
To determine whether these two courses of treatment with ocrelizumab correct the B-cell tolerance defects in patients with relapsing MS.

## Investigational plan

### Study design

This is an open label, single-arm study of anti-CD20 antibody, ocrelizumab in people with relapsing MS. Patients who fulfill the eligibility criteria will undergo blood draw for collection of peripheral blood mononuclear cells (PBMC). Participants will receive two infusions of ocrelizumab (300 mg) two weeks apart and then six months later (one infusion of 600 mg of ocrelizumab), according to the medication label and the standard of care. Baseline brain, cervical and thoracic MRI will be obtained about 12 weeks after the first course of treatment. Participants will be followed with clinical visits at least twice a year (or more frequently, if needed) and brain MRI (every six months) and cervical and thoracic spine MRI, at least annually, up to two and a half years after the baseline MRI.

The trial design is depicted in the following diagram:

### Rationale of study design

The reason we chose a single arm, open label study, as opposed to a blinded controlled study is because the latter does not help with answering our research question. Our research question is if two courses of treatment with anti-CD20 antibodies have long lasting effects on the suppression of the disease activity. One thought regarding a controlled trial design would be a non-inferiority trial with the control group continuing the use of anti CD20 treatment (every 6 months), similar to the current practice. However, as we mentioned above, continued use of B-cell depleting antibodies is extremely capable in suppressing the disease activity and in our opinion, there is no equipoise about the ability of continued B-cell depletion in completely suppressing the disease activity. However, as we argued earlier, continued use of these antibodies have known and unknown long-term side effects and a three-year trial will not be able to demonstrate the long-term safety. Also, the cost of continuous treatment is not comparable to the treatment with only two courses of antibody infusion.

### End of Study Definition

A participant is considered to have completed the study if he or she has completed all phases of the study including the last visit or the last scheduled procedure shown in the diagram above.

### Study Population

Participants will be recruited at the Johns Hopkins MS Center. We will recruit about 10 patients with relapsing MS who are naïve to DMTs or have been on injectable DMTs (interferons or glatiramer acetate) or have been off of natalizumab, fingolimod or dimethyl fumarate for at least three months and have at least 2 Gd-enhancing lesions on the brain and/or spinal cord MRI on a scan obtained in three months prior to enrollment.

Version: 2.0

Date: 3/8/2019

#### Inclusion criteria:

- Age 18 years and older.
- Diagnosis of RRMS based on revised McDonald criteria
- At least two Gd-enhancing lesions on the brain or spinal cord MRI done in the prior three months
- Naïve to disease modifying therapies or using an injectable therapy (interferons or glatiramer acetate); or, if history of receiving natalizumab, fingolimod, dimethyl fumarate and teriflunomide, no exposure for past three months
- Expanded Disability Status Scale (EDSS) score at the time of screening = <3

#### Exclusion criteria:

- Contraindication to treatment with anti-CD20 antibodies, including being seropositive for HBsAg or HIV antibody or T-spot (or Quantiferon-Gold) positive
- Ever received B-cell depleting antibodies (rituximab, ocrelizumab, ofatumumab), alemtuzumab, daclizumab, mitoxantrone or hematopoietic stem-cell transplant
- Female who are pregnant, nursing or unwilling to use contraception up to six months after the second course of the infusion (or 12 months after the first infusion)
- Treatment with steroids in the past 30 days
- Clinically unstable medical or psychiatric disorders at the time of screening that require acute treatment as determined by the PI

#### SCREEN FAILURES

Screen failures are defined as participants who consent to participate in the clinical trial but do not subsequently receive the study intervention or enter in the study. A minimal set of screen failure information is required to ensure transparent reporting of screen failure participants, to meet the Consolidated Standards of Reporting Trials (CONSORT) publishing requirements. Minimal information includes demography, screen failure details, eligibility criteria, and any serious adverse event (SAE).

#### Intervention

##### Investigational treatments

The intervention in this study is the two courses of infusions of ocrelizumab, an FDA approved medication for relapsing MS. The patients will receive ocrelizumab 300 mg IV infusion on days one and 15, according to the standard infusion protocols. The protocols include pre-medicating with acetaminophen 650 mg orally, diphenhydramine 50 mg orally and methylprednisolone 125 mg IV. The anti-CD20 antibody infusion will be repeated in six months (single infusion of ocrelizumab 600 mg). These infusions are standard of care and are done according to the medication label. However, the infusions will not be repeated after these two courses of infusion (the first two infusion of 300 mg ocrelizumab two weeks apart is considered one course and the infusion of 600 mg of ocrelizumab six months later is considered the second course).

##### Treatment arms

This is an open label, single arm, unblinded interventional study.

##### Treatment assignment

Patients who meet eligibility criteria are offered to participate in the study. This is an open label, unblinded interventional study, in which all participants receive essentially the same intervention.

## Study intervention discontinuation and participant discontinuation/withdrawal

### Discontinuation of study intervention

The study intervention is treatment with two courses of ocrelizumab. So, discontinuation from study intervention equates to not completing two courses of treatment with ocrelizumab or restarting the ocrelizumab or starting another MS disease modifying treatment after two courses of treatment with ocrelizumab for reasons other than breakthrough disease activity. All patients started on treatment will be followed in the study. Participants are free to withdraw from participation in the study at any time upon request. If a participant is unable to obtain insurance authorization for ocrelizumab within 90 days of screening visit (absent an administrative delay or other reason that is expected to be easily resolvable), the participant will be deemed a screen failure and will be replaced.

### Lost to follow-up

A participant will be considered lost to follow-up if he or she fails to return for 3 consecutive scheduled visits and is unable to be contacted by the study staff.

The following actions must be taken if a participant fails to return to the clinic for a required study visit:

- The study staff will attempt to contact the participant and reschedule the missed visit within 1 month of the missed visits, counsel the participant on the importance of maintaining the assigned visit schedule and ascertain if the participant wishes to and/or should continue in the study. Attempts to reschedule the missed visit will continue up to 3 months after the target visit date. Beyond 3 months, the visit will be considered missed and the visit window for the next standard of care clinic visit will open.
- Before a participant is deemed lost to follow-up, the investigator or designee will make every effort to regain contact with the participant (where possible, 3 telephone calls and at least 2 attempts to reach each of their emergency contacts and, if necessary, a certified letter to the participant's last known mailing address or local equivalent methods). These contact attempts should be documented in the participant's medical record or study file.
- Should the participant continue to be unreachable (3 consecutive visits missed and no response to repeated attempts to contact), he or she will be considered to have withdrawn from the study with a primary reason of lost to follow-up.

### Schedule of events

Study visits will be conducted at the Johns Hopkins Outpatient Center (JHOC). Aside from obtaining informed consent for participation in the study and collecting peripheral blood mononuclear cells (PBMCs) and the NeuroQoL, all other procedures are part of the routine clinical and standard of care at Johns Hopkins MS Center. The only deviation from the standard of care in this study is stopping the ocrelizumab infusions after two courses. Study procedures are depicted in the following table (procedures in bold font are standard of care):

Tests and assessments	Screening visit	Infusion visits (month 0)	Month 3 (baseline)	Month 6	Month 12	Month 18	Month 24	Month 30
Informed Consent	X							
Verifying eligibility	X							

Medical history	X		X	X	X	X	X	X
Physical examination and vital signs assessment	X		X	X	X	X	X	X
Neurological examination (EDSS)	X		X	X	X	X	X	X
Blood work to assess eligibility for receiving ocrelizumab and its safety after the infusions	X		X	X	X			
OCT	X		X		X		X	
Brain MRI			X		X	X	X	X
Cervical/thoracic MRI			X		X		X	
NeuroQoL	X		X	X	X	X	X	X
Lymphocyte subset analysis			X	X	X	X		
Blood sample collection for storage and future analyses	X		X	X	X	X		
Blood draw and collection to be sent to Yale	X					X (or months 24)		
Ocrelizumab infusions		X 2 infusions two weeks apart		X 1 infusion				
Side effects assessment			X	X	X	X	X	X

### Changes in the study visits and procedures due to response to the CIVD-19 pandemic:

Considering the recent events (March 2020) surrounding the COVID-19 pandemic and JHU response, and the fact that our study participants can be particularly vulnerable to the infection with the novel coronavirus, we will implement the following changes in our study protocol to reduce the immediate hazard to our participants related to the risk of exposure to COVID-19:

- Follow-up visits, including Month 3, Month 6, Month 12 Month 18, Month 24 and Month 30 in-person visits can be replaced with telemedicine visits with the study PI.
- The medical history, symptom evaluation and side effects assessment components of the study visits will be conducted through the telemedicine visits.
- The physical examination, vital signs assessment, neurological examination, OCT and research blood sample collection for future analysis will be paused temporarily, as they would require an in-person visit and would pose a risk to the participants and the staff. They will be resumed as soon as possible, after the resumption of normal research activities at the JHU.
- The NeuroQoL quality of life assessment will be delivered to participants electronically. Secure Redcap surveys will be sent to the participants' email address. Results will be printed and filed in the study binders as usual.

Version: 2.0

Date: 3/8/2019

- The blood work to assess and monitor safety and adverse effects of the therapy, including lymphocyte subset analysis, will continue to be ordered and results will be reviewed electronically by the PI.
- Infusions of ocrelizumab: Ocrelizumab may theoretically increase the risk of infection with the novel coronavirus. Delaying the ocrelizumab infusions will be determined on a case-by-case basis by the PI.
- MRI Procedures: MRI studies may be delayed because of the delays in the ocrelizumab infusions.

**Screening visit:** PI or designee will explain the study consent to study participants, and the study visit assessments will occur after the study participants sign the consent form. Screening visit procedures include review of eligibility criteria, physical exam, neurological examination, collecting vitals, blood work for assessing eligibility (liver function tests, complete blood count, Hepatitis- B surface antigen, Hepatitis- B core antibody, HIV antibody, lymphocyte subset including CD19+ B-cells, total IgG and IgM and urine pregnancy test) and blood draw (for collecting PBMCs), and completion of Neuro-QoL adult item banks. Study participants will be enrolled into the study after the study physician confirms participants' eligibility to move forward with the study.

Obtaining the B-cell depleting antibody (ocrelizumab) and all the subsequent study visits and MRIs are part of routine and standard clinical care. If the B-cell depleting medication is not approved by the participants' insurance policy, the patient will be excluded from the study.

**MRI procedures:** MRI scans will be performed at one of the Hopkins Radiology facilities at 3T. Conventional T2/FLAIR/T1-weighted images as well as post-contrast T1-weighted images of the brain will be obtained at months 3 (baseline), 12, 18, 24 and 30. Conventional T2/STIR/T1-weighted images as well as post-contrast T1-weighted images of the cervical and thoracic spinal cord will be obtained at months 3 (baseline), 12 and 24. Similar to the standard of care, brain, cervical or thoracic spine MRIs may be done as needed if the patient develop symptoms that could be suggestive for an MS relapse (based on the evaluation by a study neurologist). The MRI scans will be read by an attending radiologist at Johns Hopkins University, and these readings will be used for making decisions regarding the presence of new T2 or Gd-enhancing lesions suggestive for re-emergence of the radiological disease activity.

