## Outcomes:

**Primary outcome:** The primary endpoint (the failure event) of this study is the time to return of disease activity after the third month post-first-infusion, objectively demonstrated by development of new T2 hyperintense lesions or Gd-enhancing lesions on the MRI or a clinical relapse. A relapse is defined as new or worsening neurologic symptom(s) with an objective change on the EDSS of at least 1.5 points for participants with baseline EDSS scores of 0 or 0.5 and at least 1-point change for participants with EDSS of 1 or more, as determined by the *examining neurologist*. Symptoms must have been attributable to MS, last  $\geq 48$  hours, been present at normal body temperature, and preceded by at least 30 days of clinical stability. If a new or worsening neurological symptom did not fulfil the above-mentioned criteria, but was associated with a corresponding new or enhancing lesion on the MRI that is done in 30 days after the start of that symptom, it is still considered a clinical relapse.

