### Secondary outcome:

**Disability:** six-month confirmed worsening or improvement of disability: We will report the proportion of patients who experience one step worsening or improvement of EDSS that is confirmed on a clinical visit six months later.

**Quality of life measures:** We will administer Neuro-QoL in the computer-adaptive test (CAT) format before the infusions and in all the subsequent clinic visits.

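### The pandemic pause on neurological examinations leaves relapse and confirmed disability without an examined EDSS, so relapses that recover during the pause may be dated late or go uncounted

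*Combined protocol and SAP*

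**What the plan says.** The section on pandemic changes allows each follow-up visit from month 3 to month 30 to be held by telemedicine. It states: "The physical examination, vital signs assessment, neurological examination, OCT and research blood sample collection for future analysis will be paused temporarily". On the end of the pause it says: "They will be resumed as soon as possible, after the resumption of normal research activities at the JHU". What continues remotely is limited: "The medical history, symptom evaluation and side effects assessment components of the study visits will be conducted through the telemedicine visits". No remote EDSS, catch-up window or rule for a missing examination is given. MRI is not among the paused items; the section says only that "MRI studies may be delayed because of the delays in the ocrelizumab infusions".

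The outcome definitions were not adapted.

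- Under Primary outcome, a new T2 or enhancing lesion is a failure in itself, alongside clinical relapse. The examined criterion for relapse is "new or worsening neurologic symptom(s) with an objective change on the EDSS of at least 1.5 points" when the baseline EDSS is 0 or 0.5, with a 1-point threshold when it is 1 or higher, as judged by the examining neurologist. Failing that, symptoms still count as a relapse if an MRI within 30 days of onset shows a matching lesion.
- Under MRI procedures, the symptom-driven scan is permitted rather than required: "MRIs may be done as needed if the patient develop symptoms that could be suggestive for an MS relapse".
- Under Secondary outcome, a one-step EDSS worsening or improvement must be "confirmed on a clinical visit six months later".
- Under Statistical analysis, the primary endpoint is shown by a Kaplan-Meier curve, and the proportions with relapse, new MRI activity and disability progression are also reported separately. No censoring or missing-assessment rule appears.

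**The concern.** The pause removes the measurement on which examiner-based relapse confirmation and confirmed disability depend, and nothing takes its place. Under no wording of the endpoint in the document can symptoms reported by video count on their own. With no rule for a relapse that was reported but never examined, the participant stays in the Kaplan-Meier risk set as event-free until something else triggers failure.

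This is a single-arm study of 10 whose question is how long disease activity stays suppressed. A failure dated late lengthens the apparent suppression, and a failure not counted raises the event-free proportion. Both push towards the study hypothesis, and there is no control arm in which the same loss would occur.

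**Working it through.** The plan gives no figure on this point to reproduce. Its one power statement (Sample size) concerns autoreactive B-cell frequencies and has no bearing on relapse ascertainment. The check is therefore a comparison of sections, then an illustration of size.

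**1. Routes to failure, and their state during the pause**

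| Route | Primary outcome | Synopsis (Assessments) and Statistical analysis | During the pause |
|---|---|---|---|
| New T2 or enhancing lesion alone | Failure | Failure | Open; scans may be delayed |
| Examination | EDSS change of 1.5 or 1 point, no deadline | Objective change, no EDSS threshold | Closed until examinations resume |
| MRI confirming symptoms | Matching lesion within 30 days of onset | Matching lesion after onset, no time limit | Open; symptom-driven scan optional |

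**2. One relapse reported by video, followed through**

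- An MRI within 30 days, scheduled or not, shows a matching lesion: counted on time.
- No such MRI, but the deficit persists: it can be confirmed by EDSS after the pause, since no deadline is set.
- No such MRI, the deficit recovers, and a later scan shows a new lesion: a primary failure, at that scan. It is not a relapse under Primary outcome. Under the Statistical analysis wording it could be one, if the lesion matches the symptoms.
- No such MRI, the deficit recovers, and no later scan shows a new lesion: lost from both the primary endpoint and the relapse proportion.

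**3. How late the next scheduled scan can be** (months from MRI procedures)

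- Brain at 3, 12, 18, 24, 30: gaps 12 − 3 = 9, then 6, 6 and 6 months.
- Cord at 3, 12, 24: gaps 12 − 3 = 9 and 24 − 12 = 12 months; none scheduled after month 24.

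Any infusion-related MRI delay adds to these.

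**4. How many primary failures could be lost**

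Expected number lost = 10 × p × f × q, where p is the true failure risk, f the share of failures starting in the pause, and q the share of those never caught by any route. The documents give none of the three. I assume p from 0.3 to 0.7 and f from 0.1 to 0.5.

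- q = 0 (every such event shows on a later scan or persists to examination): 0 lost; dates only are affected.
- q = 0.1 to 0.3: from 10 × 0.3 × 0.1 × 0.1 = 0.03 to 10 × 0.7 × 0.5 × 0.3 = 1.05 lost, which inflates the event-free proportion by 0.3 to 10.5 points.
- q = 1 (no later scan or examination ever helps): from 10 × 0.3 × 0.1 = 0.3 to 10 × 0.7 × 0.5 = 3.5 lost, or 3 to 35 points.

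Each lost failure is 1/10 = 10 points. For scale, the exact 95% confidence interval for 3 failures of 10 runs from 6.7% to 65.2%.

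**5. Confirmed disability**

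EDSS is scheduled at months 3, 6, 12, 18, 24 and 30 after screening. The six-month pairs among these are 6–12, 12–18, 18–24 and 24–30. Missing month 12, 18 or 24 removes two of the four; missing month 6 or 30 removes one. A lost pair can hide improvement as well as worsening.

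**The case against.** The strongest reply is that the primary endpoint is a composite and its MRI part survives the pause. A reader might infer that a relapse without an MRI in 30 days can never meet the endpoint and is always counted as continued suppression. The documents do not support that: a new lesion on a later scheduled scan is a failure without any relapse, examination or 30-day window, and a persisting deficit can be examined later. This stands, and it turns much of the potential loss into late dating.

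Further replies have weight:

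- The 30-day limit and the EDSS thresholds appear only under Primary outcome. The looser wording elsewhere would admit more relapses, but that is an inconsistency to resolve, not a safeguard.
- Treatment stop rules say the investigator will use MRI when a relapse is in doubt. That is a confirmation route needing no EDSS, but it serves treatment decisions and carries no 30-day limit.
- Lost to follow-up allows a missed visit to be rescheduled for up to 3 months. A visit held by telemedicine is not a missed visit, however, so this does not clearly restore the examination.
- A reader might also infer that the disability loss favours the hypothesis. It need not, because improvement is counted too.
- Remote visits are permitted, not required, and the pause is temporary. The text does not imply that any one participant would have all six visits held remotely.

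None of this supplies a rule for a relapse reported remotely and never verified.

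**Conclusion.** The point holds in a limited form. The pause removes examiner confirmation of relapse with no substitute and no analysis rule. In the primary endpoint, a relapse that recovers during the pause without a timely confirming MRI is dated late where a later scan shows a new lesion. It is lost only if no later scan shows one and no EDSS change persists. In the separately reported relapse proportion, under the Primary outcome definition, it can be missed outright. Both effects lean towards apparent suppression.

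The size cannot be fixed: neither the length of the pause nor the number of participants affected is given, nor how often a relapse leaves a lesion visible on a later scan. What can be stated is up to 9 months' delay for brain and 12 for cord on the planned scan schedule, and 10 percentage points for each lost failure. The 0.3 to 10.5 point range rests entirely on the assumed p, f and q. The disability outcome loses data without a definite direction. No figure in the plan is wrong on this account.

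**What to change.** 1. Record any suspected relapse reported by telemedicine that lacks an examination or a timely MRI as an unverified relapse, with its onset date. Keep the primary analysis as defined, and repeat the Kaplan-Meier estimate and the relapse proportion counting these as failures at symptom onset.
2. Define disability confirmation as the first in-person EDSS at least six months after the change, for worsening and improvement alike.
3. Reconcile the relapse definitions in the Synopsis, Primary outcome and Statistical analysis (30-day limit and EDSS threshold). Also reconcile the pandemic section with MRI procedures and the Treatment stop rules on how suspected relapses are verified during the pause. How they are verified clinically is for the investigators to settle; the need here is that the sections agree.

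The cost is protocol wording, one added data item and one sensitivity analysis; no extra scans or visits are required. The downside is that some symptoms that were not relapses will count as failures in the sensitivity estimate, so it should be read as the pessimistic companion to the primary result.
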